### **7.3 Lost to follow up**

A participant will be considered lost to follow up if he or she repeatedly fails to return for scheduled visits and is unable to be contacted by the study site.

The following actions must be taken if a participant fails to return to the clinic for a required study visit:

- The site must attempt to contact the participant and reschedule the missed visit as soon as possible and counsel the participant on the importance of maintaining the assigned visit schedule and ascertain whether or not the participant wishes to and/or should continue in the study.
- Before a participant is deemed lost to follow up, the Investigator or designee must make every effort to regain contact with the participant (at least 1 phone call and 1 written message to the participant), and document his/her effort (date and summary of the phone call and copy of the written message in the source documents), to complete the final evaluation. All results of these evaluations and observations, together with a narrative description of the reason(s) for removing the participant, must be recorded in the source documents. The eCRF must document the primary reason for withdrawal.

Should the participant continue to be unreachable, he/she will be considered to have withdrawn from the study with a primary reason of lost to follow up documented in the eCRF.

## **8 STUDY ASSESSMENTS AND PROCEDURES**

Study procedures and their timing are summarized in the Schedule of Activities (Section 1.3 for Part A [[Table 1-3](#)] and Part B [[Table 1-4](#)]).

Protocol waivers or exemptions are not allowed.

Immediate safety concerns should be discussed with the sponsor immediately upon occurrence or awareness to determine if the participant should continue or discontinue study medication.

Adherence to the study design requirements, including those specified in the Schedule of Activities (Section 1.3), is essential and required for study conduct.

All screening evaluations must be completed and reviewed to confirm that potential participants meet all eligibility criteria. The Investigator will maintain a screening log to record details of all participants screened and to confirm eligibility or record reasons for screening failure, as applicable.

Procedures conducted as part of the participant's routine clinical management (eg, blood count) and obtained before signing of the ICF may be utilized for screening or baseline purposes provided the procedures met the protocol-specified criteria and were performed within the time frame defined in the Schedule of Activities (Section 1.3).

The maximum amount of blood collected from each participant over the duration of the study, including any extra assessments that may be required, will not exceed 500mL. Repeat or unscheduled samples may be taken for safety reasons or for technical issues with the samples.

## **8.1 Efficacy assessments**

Not applicable.

## **8.2 Safety assessments**

Planned time points for all safety assessments are provided in the Schedule of Activities (Section 1.3 for Part A [[Table 1-3](#)] and Part B [[Table 1-4](#)]).

### **8.2.1 Physical examination**

Physical examinations will be performed at the scheduled time points presented in Section 1.3 for Part A ([Table 1-3](#)) and Part B ([Table 1-4](#)).

A complete physical examination will include, at a minimum, general appearance; ear, nose, and throat; eyes, hair, and skin; and assessments of the cardiovascular, respiratory, gastrointestinal, neurological (including sensation, muscle strength, reflexes, balance and mental state), musculoskeletal, and hepatic systems.

Height and weight will be measured and recorded at the Screening Visit, and the study participant's BMI will be calculated. Height will be measured with the study participant not wearing shoes, and the outcome will be rounded to the nearest 1cm. Body weight will be measured with the study participant wearing light clothing and without wearing shoes; the outcome will be rounded to the nearest 0.1kg. The BMI will be calculated (weight [kg]/[height (m^2)]) and will be reported to 1 decimal place.

A symptom-directed physical examination will include, at a minimum, assessments of the skin, lungs, cardiovascular system, and abdomen (liver and spleen). A physical examination of the skin will include, at a minimum, a visual check of the skin, and may be conducted by a nurse or physician.

Investigators and site staff should pay special attention to clinical signs related to previous serious illnesses.

Clinically relevant findings or worsening of previous findings will be recorded as AEs.

## **8.2.2 Vital signs**

Vital signs, including pulse rate, systolic blood pressure (SBP), diastolic blood pressure (DBP), respiratory rate, and tympanic body temperature will be measured with a completely automated device after 5 minutes of rest in a supine position (in a quiet setting without distractions such as a television or cell phones). Pulse rate, SBP, and DBP will be measured with a completely automated device. Manual techniques will be used only if an automated device is not available. Any clinically significant abnormality in the view of the Investigator will be recorded as an AE.

Vital signs (to be taken before blood collection for laboratory tests) will be measured in triplicate. The mean values will be calculated and recorded on the eCRF. The vital signs will consist of 3 pulse rates and 3 blood pressure (BP) measurements (3 consecutive BP readings will be recorded at intervals of at least 1 minute).

Vital signs will be performed at the scheduled time points presented in Section 1.3 for Part A ([Table 1-3](#)) and Part B ([Table 1-4](#)).

## **8.2.3 Electrocardiograms**

Single 12-lead ECG recordings will be obtained as outlined in the Schedule of Activities in Section 1.3 for Part A ([Table 1-3](#)) and Part B ([Table 1-4](#)) using an ECG machine that automatically calculates the pulse rate and measures PR, QRS, QT, and QTcF intervals. Refer to Section 7.1.2 for QTcF withdrawal criteria and any additional QTc readings that may be necessary.

The study participant should be resting in the supine position for at least 10 minutes before the start of the recordings.

The Investigator should review all ECG recordings and, if there are abnormalities that are considered clinically significant for a particular study participant, then the Investigator should initiate a review by a specialist of all ECG data pertaining to that study participant. The following ECG parameters will be recorded in the eCRF: heart rate, PR-interval, QRS-duration, QT-interval, QTcF, and Investigator's conclusion on ECG profile.

## **8.2.4 Clinical safety laboratory assessments**

See Appendix 2 (Section 10.2) for the list of clinical laboratory tests to be performed and to the Schedule of Activities (Section 1.3 for Part A [[Table 1-3](#)] and Part B [[Table 1-4](#)]) for the timing and frequency.

The Investigator must review the laboratory report, document this review, and record any clinically relevant changes occurring during the study in the AE section of the eCRF. The laboratory reports must be filed with the source documents. Clinically significant abnormal laboratory findings are those which are not associated with the underlying disease, unless judged by the Investigator to be more severe than expected for the study participant's condition.

All laboratory tests with values considered clinically significantly abnormal during participation in the study or within 14 days after the final dose of study medication should be repeated until the values return to normal or Baseline or are no longer considered clinically significant by the Investigator or UCB Study Physician.

If such values do not return to normal/Baseline within a period of time judged reasonable by the Investigator, the etiology should be identified and the UCB Study Physician notified.

All protocol-required laboratory assessments, as defined in Appendix 2 (Section 10.2), must be conducted in accordance with the laboratory manual and the Schedule of Activities (Section 1.3).

If laboratory values from nonprotocol-specified laboratory assessments performed at the institution's local laboratory require a change in study participant management or are considered clinically significant by the Investigator (eg, SAE or AE or dose modification), then the results must be recorded in the eCRF.

### **8.2.5        Suicidal risk monitoring**

Suicidal risk monitoring is not applicable for this single-dose study.

## **8.3            AEs and SAEs**

The definitions of an AE or SAE can be found in Appendix 3 (Section 10.3).

Adverse events will be reported by the participant (or, when appropriate, by a caregiver or surrogate).

The Investigator and any designees are responsible for detecting, documenting, and recording events that meet the definition of an AE or SAE and remain responsible for following up AEs that are serious, considered related to the study medication or study procedures, or that caused the participant to discontinue UCB0599 (see Section 7).

Note that in this case the national recommendation for reporting AEs related to COVID-19 vaccines should be followed.

For results disclosure on public registries (eg, ClinicalTrials.gov), TEAEs and treatment emergent SAEs will be published.

### **8.3.1        Time period and frequency for collecting AE and SAE information**

All AEs and SAEs will be collected from the signing of the ICF until the SFU Visit at the time points specified in the Schedule of Activities (Section 1.3 for Part A [[Table 1-3](#)] and Part B [[Table 1-4](#)]).

In order to ensure complete safety data collection, all AEs occurring during the study (ie, after the signing of the ICF), including any pretreatment and posttreatment periods required by the protocol, must be reported in the eCRF even if no study medication was taken but specific study procedures were conducted. This includes all AEs not present prior to the initial visit and all AEs that recurred or worsened after the initial visit.

All SAEs will be recorded and reported to the sponsor or designee within 24 hours, as indicated in Appendix 3 (Section 10.3). The Investigator will submit any updated SAE data to the Sponsor within 24 hours of it being available.

The Investigator is specifically requested to collect and report to UCB (or its representative) any SAEs (even if the Investigator is certain that they are in no way associated with the study medication), up to 30 days from the end of the study for each participant, and to also inform participants of the need to inform the Investigator of any SAE within this period. Serious AEs that the Investigator thinks may be associated with the study medication must be reported to UCB regardless of the time between the event and the end of the study.

The method of recording, evaluating, and assessing causality of AE and SAE and the procedures for completing and transmitting SAE reports are provided in Appendix 3 (Section 10.3).

### **8.3.2 Method of detecting AEs and SAEs**

Care will be taken not to introduce bias when detecting AEs and/or SAEs. Open-ended and non-leading verbal questioning of the participant is the preferred method to inquire about AE occurrences.

### **8.3.3 Follow up of AEs and SAEs**

After the initial AE/SAE report, the Investigator is required to proactively follow each participant at subsequent visits/contacts. All SAEs and nonserious AESIs (as defined in Section 8.3.6), will be followed until resolution, stabilization, the Investigator determines that it is no longer clinically significant, the event is otherwise explained, or the participant is lost to follow up (as defined in Section 7.3). Further information on follow up procedures is given in Appendix 3 (Section 10.3).

### **8.3.4 Regulatory reporting requirements for SAEs**

Prompt notification by the Investigator to the UCB Study Physician of a SAE is essential so that legal obligations and ethical responsibilities towards the safety of study participants and the safety of an study medication under clinical investigation are met.

The Sponsor has a legal responsibility to notify both the local regulatory authority and other regulatory agencies about the safety of a study medication under clinical investigation. The Sponsor will comply with country-specific regulatory requirements relating to safety reporting to the regulatory authority, Independent Ethics Committee (IEC), and Investigators.

Investigator safety reports must be prepared for suspected unexpected serious adverse reactions (SUSAR) according to local regulatory requirements and Sponsor policy and forwarded to Investigators as necessary.

An Investigator who receives an Investigator safety report describing a SAE or other specific safety information (eg, summary or listing of SAEs) from the Sponsor will review and then file it along with the UCB0599 IB and will notify the Institutional Review Board (IRB)/IEC, if appropriate according to local requirements.

### **8.3.5 Pregnancy**

Details of all pregnancies in female participants and, if consented, female partners of male participants will be collected after the start of study medication and until at least 12 months after the delivery date.

If a pregnancy is reported, the Investigator must immediately inform the Sponsor within 24 hours of learning of the pregnancy and should follow the procedures outlined in Appendix 4 (Section 10.4).

The participant should be withdrawn from the study as soon as pregnancy is known (by positive pregnancy test [ie, a positive urine test confirmed with a blood test]), and the following should be completed:

- The participant should return for an ETV.

- The participant should immediately stop the intake of the study medication as instructed at the ETV.
- An SFU Visit should be scheduled approximately 10 days after the participant has discontinued her study medication.

Abnormal pregnancy outcomes (eg, spontaneous abortion, fetal death, stillbirth, congenital anomalies, ectopic pregnancy) are considered SAEs.

### **8.3.6 AESIs**

An AESI is any AE that a regulatory authority has mandated be reported on an expedited basis, regardless of the seriousness, expectedness, or relatedness of the AE to the administration of a UCB product/compound.

For UCB0599, the following events require immediate reporting (within 24 hours regardless of seriousness) to UCB:

- Hy's Law
  - Potential Hy's Law, defined as  $\geq 3 \times \text{ULN}$ , ALT or AST with coexisting  $\geq 2 \times \text{ULN}$  total bilirubin in the absence of  $\geq 2 \times \text{ULN}$  ALP, with no alternative explanation for the biochemical abnormality (ie, without waiting for any additional etiologic investigations to have been concluded). Follow up information should be reported if an alternative etiology is identified during investigation and monitoring of the participant.
- Hypersensitivity reactions (such as rash, angioedema, or anaphylaxis)

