**Table 1-3: Part A Schedule of activities**

Procedure	Screening	Treatment Period 1—6 a													SFU b / ETV
		In-Clinic Period													
	D-28 to D-2	D-1	D1	D2 to D5	D6	D7 to D10	D11	D12 to D18 c	D19	D20 to D23	D24	D25 to D28	D29	D30 to D33	Day 37 (± 2 days)

c The blood pregnancy test will be done at the Screening Visit and the urine pregnancy test will be done on all other occasions.

f Blood hematology and chemistry laboratory tests will be obtained in the fasting state following an overnight fast of at least 10 hours. Urinalysis includes standard analysis, microscopy, and renal biomarker analysis. For the AKI biomarkers, analysis should be performed on the fresh urine sample. Spot analysis will be performed on either fresh urinalysis sample or 24 hours urine sample, as noted.

g Only performed on Day 14 and Day 33.

h A COVID-19 test will take place per site standard to allow flexibility in the event the COVID-19 response plan changes throughout the study (ie, frequency of testing).

i During the Screening Period, at Baseline (only if the ECG was done more than 3 days before screening [between D-28 and D-2, inclusive]), and on Day 1, the 12-lead ECG (single recordings) will be performed after a rest of at least 10 minutes predose and 2 hours after dosing. If there are abnormalities that are considered clinically significant for a particular study participant, ECG recordings will be performed in triplicate at 2- to 3-minute intervals (3 ECGs within a 5-minute timeframe) prior to the exclusion of the participant (Section 7.1.2).

j Systolic and diastolic blood pressure, respiration rate, pulse rate, and tympanic body temperature will be assessed. Vital signs will be performed after a rest of at least 5 minutes predose, then 30 min, and 2 hours after study medication dosing on Day 1, Day 6, Day 11, Day 19, Day 24, and Day 29. Vital signs (to be taken before blood collection for laboratory tests) will consist of 3 pulse rates and 3 blood pressure (BP) measurements (3 consecutive BP readings will be recorded at intervals of at least 1 minute).

k An IRT will be used for assigning eligible participants to a treatment regimen based on a predetermined production randomization and/or packaging schedule provided by UCB (or designee) (Section 6.3).

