**Table 1-4: Part B Schedule of Activities**

Procedure	Screening	Treatment Period 1				Treatment Period 2			SFU a /ETV
		In-Clinic Period				In-Clinic Period			
	D-28 to D-2	D-1	D1	D2-4	D5	D6	D7-9	D10	D13 (±2 days)
Informed consent	X								
Verification of inclusion/exclusion criteria	X	X							
Demography (height, weight, BMI)	X								
Physical examination	X	X			X			X	X
General medical/procedure history	X	X							
Pregnancy test b (females only)	X	X							X
Laboratory assessments (hematology, clinical chemistry, and urinalysis) c	X	X			X			X	X
SARS-CoV-2 testing (PCR) d		X							
Viral serology (HBsAg, HCV-Ab, and HIV)	X								
Urine cotinine, drug screen, and alcohol breath test	X	X							
12-lead ECG e	X	X	X	X		X	X		X
Vital signs f	X	X	X	X	X	X	X	X	X
Randomization g		X							
Study medication administration g			X			X			
Adverse event review	X	X	X	X	X	X	X	X	X
Concomitant medication review	X	X	X	X	X	X	X	X	X
Blood sampling for PK h			X	X	X	X	X	X	

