**Figure 7-1: Phase I Liver Chemistry Stopping Algorithm**

ALT=alanine transaminase; ULN=upper limit of normal

Specific assessments and follow up actions for potential drug-induced liver injury (PDILI) are provided in Appendix 6 (Section 10.6).

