### Protocol-required safety laboratory assessments

Laboratory Assessments	Parameters			
Hematology a	Platelet count	Red blood cell indices: Mean corpuscular volume Mean corpuscular hemoglobin % Reticulocytes	White blood cell count with differential: Neutrophils Lymphocytes Monocytes Eosinophils Basophils	
	Red blood cell count			
	Hemoglobin			
	Hematocrit			
Clinical Chemistry a b	Blood urea nitrogen	Potassium	Aspartate Aminotransferase / Serum Glutamic-Oxaloacetic Transaminase	Total and direct bilirubin
	Creatinine	Sodium	Alanine Aminotransferase / Serum Glutamic-Pyruvic Transaminase	Total Protein
	Glucose (fasted)	Calcium	Alkaline phosphatase	
Routine Urinalysis c	

• Specific gravity

• pH, glucose, protein, blood, ketones, bilirubin, urobilinogen, nitrite, leukocyte esterase by dipstick

• Microscopic examination (if blood or protein is abnormal)

• Renal biomarker analysis

			
Other Screening Tests	

• Follicle-stimulating hormone (FSH) and estradiol (as needed in women of non-childbearing potential only)

• Urine drug screen (to include at minimum: amphetamines, barbiturates, cocaine, opiates, cannabinoids, methadone, and benzodiazepines)

• Serum and urine human chorionic gonadotropin (hCG) pregnancy test (as needed for women of childbearing potential)d

• Serology (HIV antibody, HBsAg, and hepatitis C virus antibody)

 
All study-required laboratory assessments will be performed by a central laboratory. The results of each test must be entered into the eCRF.
			

Laboratory Assessments	Parameters
------------------------	------------

- a Blood hematology and chemistry laboratory tests will be obtained in the fasting state following an overnight fast of at least 10 hours.
- b Details of liver chemistry stopping criteria and required actions and follow up assessments after liver stopping or monitoring event are given in Section 7.1.1 and Appendix 6 (Section 10.6). All events of ALT  $\geq 3 \times$  upper limit of normal (ULN) and bilirubin  $\geq 2 \times$  ULN ( $>35\%$  direct bilirubin) or ALT  $\geq 3 \times$  ULN and international normalized ratio (INR)  $>1.5$ , if INR measured, may indicate severe liver injury (possible Hy's Law) and must be reported as a SAE (excluding studies of hepatic impairment or cirrhosis).

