**Table 10-1: Phase 1 Liver Chemistry Stopping Criteria and Follow up Assessments Table**

Liver Chemistry Stopping Criteria	
Required Actions and Follow up Assessments	
Actions	Follow up Assessments

ALT-absolute
 
ALT <math>\geq</math>3xULN If ALT <math>\geq</math>3xULN AND bilirubin <math>\geq</math>2xULN (>35% direct bilirubin) or INR <math>></math>1.5, report as a SAEa,b See additional actions and follow up assessments below
	

• Immediately discontinue study intervention

• Report the event to the Sponsor within 24 hours

• Complete the liver event eCRF, and complete an SAE data collection tool if the event also met the criteria for an SAEb

• Perform liver function follow up assessments

• Monitor the participant until liver function test abnormalities resolve, stabilize, or return to baseline (see MONITORING)

 

• Viral hepatitis serologyc

• Obtain INR and recheck with each liver chemistry assessment until the transaminases values show downward trend

• Obtain blood sample for PK analysis at predose and at 0.25, 0.5, 1, 1.5, 2, 4, 8, 12, 24, 36, 48, 72, and 96 hours after the most recent dose of UCB0599d

• CPK and LDH

• Fractionate bilirubin, if total bilirubin <math>\geq</math> 2xULN

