**Table 10-1: Phase 1 Liver Chemistry Stopping Criteria and Follow up Assessments Table**

 
Consider the need for a toxicology screening.
 
 
MONITORING:
 
If <math>\text{ALT} \geq 3 \times \text{ULN}</math> AND <math>\text{bilirubin} \geq 2 \times \text{ULN}</math> or <math>\text{INR} > 1.5</math>:
 
 
Repeat liver function tests (include ALT, AST, alkaline phosphatase, bilirubin) and perform liver function follow up assessments within 24 hours.
 
Monitor participant twice weekly until liver function test abnormalities resolve, stabilize, or return to baseline.
 
A specialist or hepatology consultation is recommended.
 
 
If <math>\text{ALT} \geq 3 \times \text{ULN}</math> AND <math>\text{bilirubin} < 2 \times \text{ULN}</math> and <math>\text{INR} \leq 1.5</math>:
 
 
Repeat liver function tests (include ALT, AST, alkaline phosphatase, bilirubin) and perform liver function follow up assessments within 24 to 72 hours.
 
Monitor participants weekly until liver function abnormalities resolve, stabilize, or return to baseline
 
	
 
Complete blood count with differential to assess eosinophilia
 
Record the appearance or worsening of clinical symptoms of liver injury, or hypersensitivity, on the AE CRF
 
Record use of concomitant medications (including acetaminophen, herbal remedies, and other over-the-counter medications) on the concomitant medications CRF
 
Record alcohol use on the liver event alcohol intake CRF
 
 
If <math>\text{ALT} \geq 3 \times \text{ULN}</math> AND <math>\text{bilirubin} \geq 2 \times \text{ULN}</math> or <math>\text{INR} > 1.5</math>:
 
 
Anti-nuclear antibody, anti-smooth muscle antibody, Type 1 anti-liver kidney microsomal antibodies, and quantitative total IgG or gamma globulins
 
Serum acetaminophen adduct HPLC assay (quantifies potential acetaminophen contribution to liver injury in participants with definite or likely acetaminophen use in the preceding week [James, 2009])
 
 
NOTE: Not required in China.
 
 
Liver imaging (ultrasound, magnetic resonance, or computerized tomography) and/or liver biopsy to evaluate liver disease; complete liver imaging and/or liver biopsy CRFs
 

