--	---

AE=adverse event; ALT= alanine aminotransferase; AST=aspartate transaminase; CPK=serum creatine

phosphokinase; CRF=case report form; HPLC=high performance liquid chromatography;

IgG= immunoglobulin G; INR=international normalized ratio; LHD=lactate dehydrogenase;

PK=pharmacokinetic(s); SAE=serious adverse event; ULN=upper limit of normal

a Serum bilirubin fractionation should be performed if testing is available. If serum bilirubin fractionation is not immediately available, discontinue study intervention if  $\text{ALT} \geq 3 \times \text{ULN}$  and  $\text{bilirubin} \geq 2 \times \text{ULN}$ . Additionally, if serum bilirubin fractionation testing is unavailable, **record the absence/presence of detectable urinary bilirubin on dipstick** which is indicative of direct bilirubin elevations suggesting liver injury.

b All events of  $\text{ALT} \geq 3 \times \text{ULN}$  and  $\text{bilirubin} \geq 2 \times \text{ULN}$  ( $>35\%$  direct bilirubin) or  $\text{ALT} \geq 3 \times \text{ULN}$  and  $\text{INR} > 1.5$  may indicate severe liver injury (**possible 'Hy's Law'**) and **must be reported as an SAE (excluding studies of hepatic impairment or cirrhosis)**. The INR measurement is not required and the stated threshold value will not apply to participants receiving anticoagulants.

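### A potential Hy's Law case met through AST rather than ALT triggers no automatic stop, fixed work-up or mandatory SAE report in the visible protocol text; judgment-based safeguards still apply (minor)

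*Protocol*

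**What the plan says.** Protocol Section 8.3.6 makes potential Hy's Law an adverse event of special interest, reportable to the sponsor within 24 hours. The definition is a threefold rise in "ALT or AST with coexisting" total bilirubin of at least 2×ULN, without ALP of 2×ULN or more and without another explanation. SAP Section 6.1.6 repeats it.

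The action rules are written differently. Table 10-1 in Appendix 6 has one stopping row, ALT ≥3×ULN. Its first action is "Immediately discontinue study intervention", followed by a checklist that includes INR, viral hepatitis serology and timed repeat tests. Both monitoring branches start from ALT ≥3×ULN. The milder branch, with bilirubin below 2×ULN and INR no higher than 1.5, still requires the site to "Monitor participants weekly until liver function abnormalities resolve, stabilize, or return to baseline". AST appears in the table only as a test to repeat.

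The SAE rule in Appendix 2 footnote b covers ALT ≥3×ULN with bilirubin ≥2×ULN (more than 35% direct) or with INR >1.5. Such events "may indicate severe liver injury (possible Hy's Law) and must be reported as a SAE". Table 10-1 footnote b gives the same ALT-based rule.

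Section 7.1.1 requires a permanent stop once the liver criteria are met and refers to Figure 7-1. That figure is not shown in the public copy. Its abbreviation line reads "ALT=alanine transaminase; ULN=upper limit of normal".

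**The concern.** The protocol has one definition of its most serious liver signal and a narrower set of triggers for acting on it. A case that qualifies through AST alone is named as potential Hy's Law but falls outside the rules that would stop dosing, fix the work-up and require SAE reporting without anyone having to decide.

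The ordering is also odd. A participant with ALT ≥3×ULN and bilirubin below 2×ULN is stopped and worked up automatically. The AST case, with the bilirubin rise that makes it a Hy's Law candidate, is not.

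At stake is how uniformly a rare event is handled in healthy volunteers who may have doses still to come. No PK endpoint or planned analysis is affected.

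**Working it through.** No sample size, power or error rate is involved. The check takes one participant profile through each liver rule, then counts the doses that follow a scheduled laboratory test.

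**Step 1: the rules side by side.** The AST case has AST ≥3×ULN, ALT <3×ULN, total bilirubin ≥2×ULN, ALP <2×ULN and no alternative explanation. The comparison case has ALT ≥3×ULN, bilirubin <2×ULN and INR ≤1.5.

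| Rule | Trigger as written | AST case | Comparison case |
|---|---|---|---|
| Section 8.3.6 special-interest event | ALT or AST, with bilirubin | Met | Not met |
| Table 10-1 stop | ALT ≥3×ULN | Not met | Met |
| Table 10-1 work-up and monitoring | ALT ≥3×ULN | Not met | Met |
| Compulsory SAE rule (both footnotes b) | ALT ≥3×ULN with bilirubin or INR | Not met | Not met |
| Appendix 3, important medical events | Potential Hy's law named as an example | Normally serious, by judgment | Not named |
| Appendix 6 assessment of potential drug-induced liver injury | No analyte named | Applies; the stop is a decision | Applies |
| Figure 7-1 | Not shown | Unknown | Unknown |

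The AST case meets the definition and none of the visible compulsory triggers.

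**Step 2: where an automatic stop could act, Part A.** Doses are on Days 1, 6, 11, 19, 24 and 29 (Table 1-1). Table 1-3 footnote g says of the in-treatment laboratory tests: "Only performed on Day 14 and Day 33". Only Day 14 precedes further dosing.

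- Doses left after Day 14: 3 of 6 (Days 19, 24, 29).
- Time to the next dose: 19 − 14 = 5 days.
- With 42 randomized: 42 × 3 = 126 of 42 × 6 = 252 planned doses.
- With 36 completers: 36 × 3 = 108 of 36 × 6 = 216.

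**Step 3: the same for Part B.** Doses are on Days 1 and 6. Table 1-4 schedules in-treatment laboratory tests on Days 5 and 10, and only Day 5 precedes a dose.

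- Active participants: 4 per active sequence × 3 sequences × 2 origins = 24.
- Doses left after Day 5: 24 × 1 = 24 of 24 × 2 = 48 planned active doses, before replacements.
- Time to the next dose: 6 − 5 = 1 day.

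For results from Part A Day 33, Part B Day 10 or the follow-up visit, no dose remains, so only the work-up and SAE status are affected.

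**The case against.** The strongest reply is that such a participant would not slip through.

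- The event reaches the sponsor within 24 hours, the same clock as an SAE.
- Appendix 6 requires any potential drug-induced liver injury to be assessed for discontinuation.
- Section 6.7 stops dosing for a laboratory abnormality that the investigator judges to compromise safety, and Section 7.1.1 also allows a stop on investigator judgment.
- Section 8 sends immediate safety concerns to the sponsor for a decision on continuing.
- Appendix 3 names potential Hy's law among events normally treated as serious, without an ALT limit.
- In Part B, Section 7.1.5 halts dosing after one SAE judged related, subject to case review. That is broader than stopping one participant.

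All of this stands, and it makes unnoticed re-dosing unlikely. Each step does rest on someone's judgment, which a compulsory trigger does not.

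A second reply concerns Figure 7-1. The figure is missing, and abbreviation lines in this protocol are not complete indexes: the one under Table 10-1 omits HBsAg, which its own footnote c uses. This stands too. The line fits an ALT-only algorithm but does not prove one.

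A third is that Section 7.1.1 sends potential drug-induced liver injury to Appendix 6 without naming an analyte, so a careful site would use the only checklist there. It may, but as written the checklist opens from ALT ≥3×ULN.

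A reader might infer that AST cases are left unprotected, that SAE status is ruled out, or that 126 and 24 doses are at risk. The documents support none of these. The safeguards above apply, Appendix 3 presumes seriousness, and the counts are of all later planned doses.

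**Conclusion.** The mismatch is real and minor. In the visible text an AST-only potential Hy's Law case lacks an automatic stop, a fixed work-up and a compulsory SAE report. It does not lack protection.

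Confidence is high that Table 10-1 and both SAE footnotes name ALT only. It is medium for the stop, because that also depends on Figure 7-1. If the figure includes AST, the stop limb weakens and what remains is that Table 10-1 should match it.

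The counts of 126 of 252 and 24 of 48 show where a stop could act, assuming the scheduled tests only and full enrolment. The documents give no event rate. Frequency should be low, since Section 5.2 excludes ALT, AST or ALP above ULN at screening.

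**What to change.** 1. In Table 10-1, add AST ≥3×ULN with total bilirubin ≥2×ULN meeting the Section 8.3.6 definition as a trigger for discontinuation and work-up. Make the same change in Figure 7-1 if it is ALT-only, so that the two agree.
2. In Appendix 2 footnote b and Table 10-1 footnote b, extend the possible Hy's Law SAE rule to ALT or AST. Keep the >35% direct-bilirubin condition, so that isolated indirect hyperbilirubinaemia such as Gilbert's syndrome, which Section 5.2 allows at entry, is not swept in. An AST case with a lower direct fraction would stay outside the compulsory rule, exactly as an ALT case does now.
3. Optionally, flag in the SAP Section 6.1.6 listing which definition each participant met. This changes no result: the adverse event listing in SAP Section 5.5.2 already flags SAEs and events of special interest.

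The cost is wording. AST and total and direct bilirubin are already in the Appendix 2 panel, so no new test is needed. The downside is slightly more dosing stops and SAE reports for rare events, and a related SAE could set off the Part B halt. The added stop is no stricter than the current one, which already applies to any ALT ≥3×ULN whatever the bilirubin.
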